5.6. Safety Analyses

All safety analyses for double-blind phase will be based on the safety analysis set based on actual intervention received, unless otherwise specified. All safety analyses for the open-label treatment/observation phase will be based on open-label analysis set and observation analysis set based on participants receiving esketamine or SOC only, respectively, in this phase. Safety analyses for the follow-up analysis phase will be based on the safety analysis set.

For all continuous safety variables, descriptive statistics by intervention group will include the N, mean, standard deviation, median, minimum, and maximum. Categorical variables will be summarized by intervention group using frequency counts and percentages.

5.6.1. Extent of Exposure

The number and percentage of participants who receive each study agent within a study intervention will be summarized by phase.

Descriptive statistics for duration of each study agent within a study intervention (N, mean, SD, median, and range [minimum, maximum]) will be summarized by phase.

Duration of intervention will be summarized for the double-blind phase in the following duration categories: ≤7 days, 8-14 days, 15-21 days, 22-25 days, >25 days for each study agent within a study intervention.

Duration of intervention will be summarized for the open-label treatment phase in the following duration categories: ≤28 days, 29-56 days, 57-84, >84 days for participants receiving open-label esketamine study intervention.

Study intervention duration is defined as (date of last dose of study intervention – date of first dose of study intervention) +1.

Total dose days of intervention is defined as the total number of days that study intervention was administered to the participant (excluding days off study intervention). Descriptive statistics for total dose days within a study intervention (N, mean, SD, median, and range [minimum, maximum]) will be summarized. A frequency distribution will also be provided.

The analysis will be performed on safety analysis set and open-label analysis set.

Patients' awareness of study intervention assignment will be summarized for the double-blind phase on the full efficacy analysis set and safety analysis set.

5.6.2. Adverse Events

The verbatim terms used in the CRF by investigators to identify adverse events will be coded using the Medical Dictionary for Regulatory Activities (MedDRA). Any AE occurring at or after the initial administration of study intervention through the day of last dose is considered to be treatment emergent. If the event occurs on the day of the initial administration of study intervention, and either event time or time of administration are missing, then the event will be assumed to be treatment emergent. If the event date is recorded as partial or completely missing, then the event will be considered to be treatment emergent unless it is known to be prior to the first administration of study intervention based on partial onset date or resolution date. All reported treatment-emergent adverse events will be included in the analysis. For each adverse event, the number and percentage of participants who experience at least 1 occurrence of the given event will be summarized by intervention group.

Assignment of adverse events to double-blind, open-label treatment/observation or follow-up phase will be made based on the following rules:

Double-blind phase:

AEs will be assigned to the double-blind analysis phase as detailed below.

- For participants who did not continue to open-label treatment/observation phase or participants who chose to be observed only (receive SOC only) in the observation phase: double-blind phase start date/time ≤AE onset date/time ≤double-blind phase end date.
- For participants who received open-label esketamine nasal spray: double-blind phase start date /time ≤AE onset date/time <double-blind phase end date/time (ie, open-label phase start date/time)
 - AEs that occur on the last day of double-blind phase but AE onset time is missing will be assigned to the double-blind phase.

AEs that are assigned to the double-blind analysis phase as detailed below will be considered as treatment-emergent.

- For participants completed double-blind treatment: all the AEs in the double-blind treatment phase will be considered as treatment-emergent for the double-blind phase.
- For participants who discontinued double-blind treatment and double-blind phase at the same time, all the AEs in the double-blind treatment phase will be considered as treatment-emergent for the double-blind phase.
- For participants who discontinued double-blind treatment but continued to be assessed until the end of double-blind phase (Day 28), AEs will be considered as treatment-emergent for the double-blind phase only if they satisfy the condition: double-blind phase start date /time ≤ AE onset date/time ≤ last day of double-blind treatment.

Open-label treatment phase:

- For participants who received open-label esketamine nasal spray, all AEs that are assigned to the open-label treatment phase will be considered as treatment-emergent if they satisfy the condition: open label treatment phase start date/time≤ AE onset date/time ≤ open label treatment phase end date.
 - AEs that occur on the last day of double-blind phase but AE onset time is after open-label dosing will be considered as treatment-emergent for the open-label treatment phase.

Observation phase:

• For participants who received SOC only in the observation phase, all AEs that are assigned to the observation phase will not be considered as treatment-emergent if they satisfy the condition: double-blind phase end date+1≤ AE onset date ≤ observation phase end date.

Follow-up phase:

• Any AEs that are assigned to the follow-up phase will not be considered as treatmentemergent. AEs during the follow-up phase should satisfy the condition: follow-up phase start date ≤AE onset date ≤follow-up phase end date.

Summary tables will be provided for adverse events by phase:

- AEs
- Serious AEs (SAEs)
- AEs leading to discontinuation of each study agent within a study intervention
- AEs by severity
- AEs by relationship to each study agent within a study intervention
- AEs of special interest

In addition to the summary tables, listings will be provided for participants who had:

- SAEs
- AEs leading to discontinuation of study intervention
- AEs of special interest

Incidence of other treatment-emergent adverse events of special interest will be summarized. See Appendix 7 for list of adverse events in each category.

The proportion of TEAEs occurring on dosing days and the proportion of TEAEs that occur on dosing days with same day resolution will be summarized. Duration and resolution time of severe TEAEs will also be summarized.

A listing of participants who died will be provided.

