Missing data in clinical trials can lead to problems that undermine the scientific credibility of causal conclusions. The most common reason for missing data is participants who discontinue the assigned treatment because of AEs, lack of tolerability, lack of efficacy, or inconvenience. In order to reduce missing data in this study, if a participant discontinues double-blind study medication for reasons other than withdrawal of consent, the participant should complete the remaining scheduled visits (without study medication dosing) through the end of the phase (Day 28). For participants remaining in the double-blind treatment phase without study medication dosing, standard-of-care treatment may be initiated. Participants who complete the double-blind treatment phase (ie, including the Day 28 visit) may be eligible to proceed to the open-label treatment/observation phase.

If a participant discontinues from the study in the double-blind treatment phase (ie, prior to completion of the Day 28 visit), an Early Withdrawal visit should be conducted within 1 week of the date of discontinuation. Participants that discontinue early from the double-blind treatment phase (ie, prior to completion of the Day 28 visit) are not eligible to participate in the open-label treatment/observation phase and will proceed to the follow-up phase.

Open-label Treatment or Observation Phase (up to 3 months)

On Day 28, following completion of the double-blind treatment phase assessments (which includes the Day 28 MADRS assessment), participants may participate in an open-label treatment/observation phase.

During the open-label treatment/observation phase, for a duration of up to 3 months, participants can:

- receive open-label esketamine nasal spray
 - If clinically indicated based on the investigator's judgment, participants receiving openlabel esketamine nasal spray treatment can also receive standard-of-care treatment for depression.

The decision to receive open-label esketamine must be made at the start of the open-label treatment/observation phase, participants who chose to not receive esketamine (to be observed only) will not be allowed to start open-label esketamine treatment during this phase.

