4. POPULATIONS (ANALYSIS SETS) FOR ANALYSIS

Analysis Sets	Description
Randomized Analysis Set	The randomized analysis set includes all participants who were randomized in the study.
Full Efficacy Analysis Set	The full efficacy analysis set includes all randomized participants who meet nonresponse criteria (List 1) and received at least 1 dose of double-blind study intervention. Four participants meeting nonresponse criteria that were incorrectly randomized to the randomization list for those participants who do not meet the predefined nonresponse criteria (List 2) due to data migration error will be included in the full efficacy analysis set.
Randomization List 2 Analysis Set	The randomization list 2 analysis set includes all randomized participants who do not meet nonresponse criteria during screening and received at least 1 dose of double-blind study intervention. Four participants meeting nonresponse criteria that were incorrectly randomized to the randomization list for those participants who do not meet the predefined nonresponse criteria due to data migration error will be excluded in the randomization list 2 analysis set.
Safety Analysis Set	The safety analysis set includes all randomized participants (both participants who meet and do not meet nonresponse criteria) who received at least 1 dose of double-blind study intervention.
Open-label Analysis Set	The open-label analysis set includes all participants who received at least 1 dose of open-label esketamine study intervention.
Observation Analysis Set	The observation analysis set includes all participants who entered the observation phase but did not receive any open-label esketamine study intervention.

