5.1.3. Analysis Phases

Double-blind Phase

The analysis reference start date of the double-blind analysis phase is the date of the first dose of double-blind study intervention. The analysis reference end date of the double-blind analysis phase is the maximum of the date of the last visit in the double-blind phase and date of early withdrawal

a. If assessment was performed as part of Visit 2.10 (on the same day) in double-blind phase, duplicate predose assessment is not required.

b. Endpoint (OBS) is only derived for CGI-S.

from the double-blind phase. For participants who entered the open-label phase and received first dose of open-label treatment after the date of last visit in double-blind phase, the analysis reference end date of the double-blind analysis phase is the date of first open-label treatment. For randomized participants who did not receive any study intervention in the double-blind phase, both analysis reference start and end dates are missing for the double-blind analysis phase.

Open-label treatment or Observation Phase

Start and end dates for the open-label treatment or observation phase are only defined for participants who participated in the open-label treatment or observation phase. The analysis reference start date of the open-label treatment or observation phase is the reference end date of the double-blind analysis phase. The analysis reference end date of the open-label treatment or observation phase is the maximum of the date of the last visit in the open-label treatment or observation phase and date of early withdrawal from the open-label treatment or observation phase. For randomized participants who did not participate in the open-label treatment or observation phase, both analysis reference start and end dates are missing for the open-label treatment or observation phase.

Follow-up Phase

Start and end dates for the follow-up phase are only defined for participants who continued into the follow-up phase. The analysis reference start date of the follow-up analysis phase is the day after the reference end date for the double-blind analysis phase (for participants who did not continue into open-label treatment or observation phase), or the open-label treatment or observation phase (for participants who participated in the open-label treatment or observation phase). The analysis reference end date of the follow-up analysis phase is the maximum of the last follow-up visit date or the disposition date at follow-up.

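### SAP 5.6.2 counts treatment-emergent events over different windows for participants who stop double-blind drug early, depending on whether they stay or leave

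*SAP*

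**What the plan says.** SAP 5.6.2 opens with a general definition: "Any AE occurring at or after the initial administration of study intervention through the day of last dose is considered to be treatment emergent". Its double-blind bullets then divide participants by disposition.

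- **Completers:** "For participants completed double-blind treatment: all the AEs in the double-blind treatment phase will be considered as treatment-emergent".
- **Leavers**, who stop drug and phase together, have the same rule: "For participants who discontinued double-blind treatment and double-blind phase at the same time, all the AEs in the double-blind treatment phase" count.
- **Stayers**, who stop drug but are followed to Day 28, have events counted "only if they satisfy the condition: double-blind phase start date /time ≤ AE onset date/time ≤ last day of double-blind treatment".

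For completers and leavers the window therefore closes with the phase. SAP 5.1.3 ends the phase at "the maximum of the date of the last visit in the double-blind phase and date of early withdrawal", or at a later first open-label dose for those who go on to one. For participants who leave the study in this phase, SAP 1.2 says that "an Early Withdrawal visit should be conducted within 1 week of the date of discontinuation".

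No bullet describes **brief stayers**, who stop drug, attend some further visits and withdraw before Day 28.

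Protocol 7.1 asks participants who stop drug, other than by withdrawing consent, to keep attending to Day 28. SAP 1.2 allows them to start standard-of-care treatment during that time.

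**The concern.** Consider an adverse event that starts between two dosing visits and is the reason the next dose is not given. The participant was on schedule when it began. Under the bullets, that event is treatment-emergent if the participant then leaves and not treatment-emergent if the participant stays, which is what the protocol requests. Classification should not turn on a choice made after onset.

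The outputs at stake are those built on treatment-emergent events: overall incidence, events of special interest, duration of severe events, and the share of events that fall on dosing days. The last is directly exposed, because the stayer cut can remove only events that start after the participant's last dosing day. Two programmers could also treat brief stayers differently and both claim to follow the SAP.

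**Working it through.** **Inputs.** Double-blind doses are on Days 1, 4, 8, 11, 15, 18, 22 and 25, with ±1 day after Day 1 (Protocol 1.3). The early-withdrawal visit falls up to 7 days after discontinuation (SAP 1.2). Phase end is as in SAP 5.1.3.

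**Window after the last dose.** Days counted = window end − last-dose day. Example: last dose Day 11, Day 15 dose not given and treatment stopped that day, early-withdrawal visit on Day 15 + 7 = Day 22 for the leaver.

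| Disposition | Window end | Days after last dose | Event on Day 13 | Event on Day 20 |
|---|---|---|---|---|
| Leaver | Day 22 | 22 − 11 = 11 | counted | counted |
| Stayer | Day 11 | 11 − 11 = 0 | not counted | not counted |
| Brief stayer | no bullet | unclear | unclear | unclear |

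If the leaver's discontinuation is instead dated to the last dose, the visit is due by Day 18 and the tail is at most 18 − 11 = 7 days. For comparison, an on-schedule completer has 28 − 25 = 3 days, or 27 − 26 = 1 to 29 − 24 = 5 with the visit windows.

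**Alternative reading of the stayer's end date.** If it means the recorded discontinuation date (Day 15), the Day 13 event counts for both. The tails still differ: 15 − 11 = 4 days for the stayer against 11 for the leaver.

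**Opening sentence against the bullets.** For the leaver, the opening sentence stops at Day 11 and the bullet at Day 22. For an on-schedule completer who takes no open-label esketamine, it stops at Day 25 and the bullet at Day 28. For a completer who does take it there is no conflict, because SAP 4 also calls that drug study intervention ("The open-label analysis set includes all participants who received at least 1 dose of open-label esketamine study intervention"), so the last dose comes later.

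**Size.** The plan gives no figure, so these are assumptions.

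- Early stoppers: applying the 20% planning drop-out rate (SAP 3) to all 446 participants gives 446 × 0.20 = 89.2, about 89.
- Treatment-ending events: Protocol 2.2 reports 4.6% on esketamine and 1.4% on placebo in the pooled adult short-term trials, both with an oral antidepressant. With 2:1:1 allocation, 223 receive esketamine and 223 placebo. 223 × 0.046 = 10.3 and 223 × 0.014 = 3.1, together 13.4, or 3.0% of 446.

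The 13 is a ceiling for treatment-ending events. Such an event is affected only if it starts after the last-dose day and the participant then stays. The documents do not give that share, so the range is 0 to about 13. They give no rate for other events after the last dose.

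**The case against.** The stayer cut may be deliberate. A stayer can start standard-of-care treatment, and off-drug follow-up can be long: after a last dose on Day 4 it is 28 − 4 = 24 days. Excluding that time is reasonable. This part stands, but it does not explain excluding the interval before the decision to stop, and the SAP gives no reason.

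The 11-day tail needs discontinuation dated to the next planned dosing visit and the early-withdrawal visit at the latest permitted time. Many leavers would have less. That limits the size, not the inconsistency.

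Protocol 2.2 describes adverse events as falling mainly on dosing days; for example, 90% to 100% of blood-pressure-increase events did. That also stands, and is why the effect is probably small.

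Three stronger readings are tempting and are not supported:

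- *A reader might infer that the stayer's end date is wholly undefined.* The opening sentence of 5.6.2 and the duration formula in 5.6.1 both use the last dose, so that is the natural meaning. Some ambiguity remains where the recorded discontinuation date is later.
- *A reader might infer that brief stayers have no rule at all.* The opening sentence can cover them through the last-dose day. What is unclear is the status of their later double-blind events, since the bullets already override that sentence for other groups.
- *A reader might infer an unlisted departure from the protocol.* Protocol 9.4.5 itself equates onset in the treatment phase with treatment-emergent events, and Section 9 leaves detail to the SAP.

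**Conclusion.** The point holds as an inconsistency in a stated rule. Among early stoppers, the same event after the last dose is treatment-emergent for a leaver and not for a stayer. The opening sentence conflicts with the leaver bullet, and with the completer bullet for completers who take no open-label esketamine. Events after the last dose in brief stayers have no clear status.

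The conclusion that an event before the decision to stop loses its status rests on reading the stayer's end date as the last-dose day. The size estimate rests on carrying earlier adjunctive-trial rates into a monotherapy trial.

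The consequence is limited. Affected events remain double-blind-phase events, and the listings of serious events and of events leading to discontinuation are not described as restricted to treatment-emergent ones. It would be wrong to infer that events disappear from the report or that one arm is favoured: the direction is unknown. Efficacy is unaffected. This is a cheap improvement.

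**What to change.** 1. State in SAP 5.6.2 that the phase-specific bullets override the opening sentence.
2. Replace the end date in the stayer bullet with a named, recorded date.
3. Use one cut for everyone who stops double-blind drug early, whether they stay, leave at once or stay briefly: onset no later than max(recorded treatment-discontinuation date, last double-blind dose + one prespecified short tail).
4. End that window early only at the first open-label dose, not at double-blind phase end. The follow-up and observation bullets, which treat no event as treatment-emergent, then need a matching exception.

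The sponsor should choose and justify the tail. Six days is one example: the longest scheduled gap is 4 days, and the ±1-day windows at each end make it 4 + 2 = 6. In the example above the cut is max(15, 11 + 6) = Day 17, so the Day 13 event counts and the Day 20 event does not, for all three groups. Capping at phase end would undo this. A leaver seen for early withdrawal on Day 15 would have a Day 16 event excluded while a stayer's counted.

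Leave the completer rule unchanged, and list separately the events whose status changes.

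**Cost.** SAP wording and one derivation in the adverse-event dataset, with no new data if the case report form records the discontinuation date (an assumption). A few early off-drug events, possibly on standard of care, are added for stayers, and a few late events are dropped for leavers. No rule can recover events that are never collected after consent is withdrawn.

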5.6.3. Additional Safety Assessments

5.6.3.1. Vital Signs and Physical Examination Findings

Descriptive statistics for values and changes from baseline at each scheduled time-point will be presented for temperature, systolic blood pressure, diastolic blood pressure, pulse rate, weight, and BMI by phase. In addition, descriptive statistics of pulse rate and blood pressure (systolic and diastolic) values, changes and percent changes from predose will be provided for each dosing day by phase. These summaries will also be provided by hypertension status (history of hypertension recorded in medical history: Yes/No). For DB and OL phases, summary statistics over time will only be provided on dosing days with the exception of Day 2 (DB) and Day 28(DB). Frequency distributions of maximum percent change increase from predose and time of maximum percent change increase will also be presented by phase. Note that if the maximum value within a phase occurs at multiple time points, the earliest time point is selected.

CONFIDENTIAL – FOIA Exemptions Apply in U.S.

E-1---- 2024

31

The proportion of participants who have a treatment-emergent abnormality, as defined in Table 7 below, will be presented over time and by phase. Both the double-blind baseline and the predose assessment will be used to determine abnormal values. A listing of participants meeting any of the criteria will also be provided.

Table /: Clinical		Clinical	iy important Abnormai	ities in vitai Signs	
	Vital Sign		Abnormal Category	Criteria	

Vital Sign	Abnormal Category	Criteria
Pulse	Abnormally high	≥100 bpm and with ≥15 bpm increase from baseline/predose
	Abnormally low	≤50 bpm and with ≥15 bpm decrease from baseline/predose
Systolic blood pressure	Abnormally high	≥180 mm Hg and with ≥20 mm Hg increase from baseline/predose
	Abnormally low	≤90 mm Hg and with ≥20 mm Hg decrease from baseline/predose
Diastolic blood pressure	Abnormally high	≥105 mm Hg and with ≥15 mm Hg increase from baseline/predose
	Abnormally low	≤50 mm Hg and with ≥15 mm Hg decrease from baseline/predose

The proportion of participants who experienced acute hypertension (systolic BP≥180 or diastolic BP≥110) at any time during the double-blind phase will be summarized by treatment group and hypertension status.

Mean (+/-SE) values for systolic BP, diastolic BP and heart rate will be presented graphically over the double-blind phase by intervention group and hypertension status. In addition, for participants with hypertension who receive antihypertensive medication, the same graphs will be summarized by medication type (beta-blockers, all other agents).

